10. STATISTICAL CONSIDERATIONS

10.1. Sample Size. Power analyses focus on estimating a sample size large enough to detect “true” effects, thereby avoiding Type II errors. Sample size estimates were obtained for intervention contrasts. Necessary sample sizes were assessed via sample size and power equations for multi-level models using the Optimal Design software program. Based on previous findings using CAA and PNF approaches, we anticipate intervention effects relative to the neutral control condition to be in the small to medium range but at least comparable to effects which have been reported for personalized normative feedback, which are typically in the .28 range (e.g., Dotson et al., 2015). Based on the proposed sample size of 600, given four assessment points, we anticipate the ability to detect effects of intervention contrasts and moderation effects across the small to medium range. Considering maximum anticipated attrition rates of 15% (N=510) we will have .70, .80, and .90 power to detect effects sizes of $\delta = .24, .27, \text{ and } .32$, respectively.

10.2. Analysis Plan. Aims will be evaluated using generalized linear mixed models, an extension of general linear models allowing for multi-level data with non-normal distributions (e.g. Atkins, Baldwin, Zheng, Gallop, & [name], 2013; Hedeker & Gibbons, 2006). With respect to evaluating main effects of experimental conditions on drinking, each participant will provide up to four assessments (baseline, 1-month, 3-month, and 6-month follow-up data). Hypotheses will be tested using specific contrast vectors, using a general linear hypothesis framework (Fox, 2008).

Hypotheses associated with Aim 1 will be evaluated examining outcomes as a function of two dummy coded variables representing CAA and PNF with control as the reference group. Time X CAA outcomes will provide direct tests of differences in change between CAA and control groups. We will utilize a Bonferroni correction with Šídák adjustment for correlated outcomes to reduce alpha inflation associated with multiple outcomes (i.e., moderation attitudes, heavy drinking attitudes, dissonance, drinks per drinking day, binge frequency, peak BAC, alcohol consequences, and PBS use).

For these analyses, each participant will provide up to 4 repeated measures (i.e., baseline, 1-month, 3- months, 6-months), yielding up to 2400 Level 1 cases (repeated-measures) across 600 Level 2

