cases). Assuming outcomes follow a negative binomial distribution with a natural log link, the following model will be the basis for evaluating intervention effects as specified in Aim 1 hypotheses:

$$\text{Level 1: } \log(E[\text{DV}]_{ti}) = \pi_{0i} + \pi_{1i}(\text{Time})_{ti} + \varepsilon_{ti} \quad \varepsilon_{ti} \sim N(0, I\sigma^2_\varepsilon)$$

$$\begin{aligned} \text{Level 2: } \pi_{0i} &= \beta_{00} + \beta_{01}(\text{site})_i + \beta_{02}(\text{CAA})_i + \beta_{03}(\text{PNF})_i + \beta_{10} + r_{00i} \\ \pi_{1i} &= \beta_{10} + \beta_{11}(\text{site})_i + \beta_{12}(\text{CAA})_i + \beta_{13}(\text{PNF})_i + r_{10i} \end{aligned}$$

where t indexes repeated-measures and i indexes participants. Campus represents the differences between Brown and UH, CAA represents the difference between CAA and the Control group, and PNF represents the difference between PNF and the control group. DV_{ti} represents the outcome vector for each individual at each assessment point. Time_{ti} measures weeks since baseline. Hypotheses associated with Aim 2 will test the relative efficacy of CAA vs. PNF using a non-inferiority design. Following the procedures outlined by Schumi & Wittes (2011), we have consulted a recent metaanalysis to obtain an effect size estimate of PNF efficacy (vs. Control) on drinking quantity ($d = .289$, 95% CI [0.117, 0.451]) and consequences ($d = .157$, 95% CI[0.037, 0.278]) (Dotson, Dunn, & Bowers, 2015). Next, we use the lower bound of each confidence interval as the basis for deriving our margin with respect to declaring non-inferiority. Thus $M1 = 0.117$ for quantity and $M1 = .037$ for consequences; these represent the most conservative estimate of the PNF effect. Then we select a smaller margin (M2) that represents the largest acceptable loss of effect when CAA is compared to PNF. Using a conservative estimate of M2 (50% of M1; USFDA, 2016), we establish non-inferiority if we retain at least half of the effect of PNF. Thus, if the lower bound confidence interval for the effect of CAA vs PNF is larger than half the lower bound estimate of the effects on drinking quantity (.117/2 = .0585) and consequences (.037/2 = .0185), we will be able to declare CAA is non-inferior to PNF.

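### The Aim 2 non-inferiority rule is wrong as written: it requires CAA to beat PNF by the margin, although the margin is defined as an acceptable loss

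*Combined protocol and SAP*

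**What the plan says.** Section 4 gives Aim 2 as a secondary hypothesis that CAA is not inferior to PNF on consumption and consequences. Section 2 presents non-inferiority to PNF as one of two results that would support CAA.

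Section 10.2 sets out the test: "Hypotheses associated with Aim 2 will test the relative efficacy of CAA vs. PNF using a non-inferiority design". From a meta-analysis it takes PNF-versus-control effects of d = 0.289 (95% CI 0.117 to 0.451) for quantity and d = 0.157 (0.037 to 0.278) for consequences. M1 is the lower confidence limit of each. M2, the "largest acceptable loss of effect when CAA is compared to PNF", is half of M1, and "we establish non-inferiority if we retain at least half of the effect of PNF". The decision rule follows: CAA is declared non-inferior "if the lower bound confidence interval for the effect of CAA vs PNF is larger than half the lower bound estimate", with 0.0585 and 0.0185 printed as the thresholds and no minus sign.

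On the model, section 10.2 says "Aims will be evaluated using generalized linear mixed models". The only model written out is introduced for Aim 1: "Assuming outcomes follow a negative binomial distribution with a natural log link", with a time variable that "measures weeks since baseline". Section 10.1, repeated in item 13 of the DSMP (Appendix E), gives power of 0.70, 0.80 and 0.90 for effects of 0.24, 0.27 and 0.32 with 510 participants.

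**The concern.** The definition of M2 and the decision rule contradict each other. If CAA may lose up to M2 relative to PNF, the lower limit for CAA minus PNF has to stay above minus M2. The printed rule asks for a lower limit above plus M2, so CAA has to be shown better than PNF by at least the margin.

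This is the only decision rule for Aim 2, and nothing elsewhere in the document corrects it. Followed literally, it almost always fails a CAA that works as well as PNF. Corrected informally once results are known, it leaves the non-inferiority claim open to challenge, because the criterion was not fixed in advance.

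Two secondary gaps are linked to it. The margins are in d units while the planned models are generalized linear mixed models, and no conversion, time point or confidence level is given for Aim 2. The stated power concerns detecting effects of 0.24 to 0.32 and does not address margins of 0.0585 and 0.0185.

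**Working it through.** **1. The plan's own figures.** M2 = 0.5 × M1: 0.117/2 = 0.0585 and 0.037/2 = 0.0185. Both reproduce.

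**2. Direction.** The paragraph reports PNF versus control as positive d for benefit. With D = CAA minus PNF on that scale, an acceptable loss of M2 means showing D > -M2. The printed rule shows D > +M2; its nominal error rate is reached when CAA is truly better than PNF by M2. Other readings do not repair it. On a raw drinking scale, where higher is worse, a lower limit above +0.0585 would show CAA to be worse. A CAA-versus-control contrast could support a retention rule, but the sentence, the definition of M2 and the opening of the Aim 2 text all name PNF as comparator.

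**3. Standard error.** From section 10.1, SE = delta/(z_alpha + z_power). Alpha is not stated, so two values are used.

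- Two-sided 0.05: 0.24/(1.960 + 0.524) = 0.0966; 0.27/(1.960 + 0.842) = 0.0964; 0.32/(1.960 + 1.282) = 0.0987.
- One-sided 0.05: 0.1106, 0.1086, 0.1093.

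Range: 0.0964 to 0.1106. A simple two-group calculation with 510/3 = 170 per arm gives sqrt(2/170) = 0.1085, inside this range. Assumption: the same SE applies to CAA versus PNF, because the arms are equal (section 6.1).

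**4. Probability of passing when CAA = PNF.** As printed: Phi(-M2/SE - z). Sign corrected: Phi(M2/SE - z). Here z = 1.96 for a 95% interval and 1.645 for a 90% interval.

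| Rule | Interval | Quantity | Consequences |
|---|---|---|---|
| As printed | 95% | 0.5-0.6% | 1.6-1.7% |
| As printed | 90% | 1.2-1.5% | 3.3-3.5% |
| Sign corrected | 95% | 8-9% | 4% |
| Sign corrected | 90% | 13-15% | 7% |

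**5. Effect of sample size.** At 1,000 per arm the SE is multiplied by sqrt(170/1000), giving 0.0397 to 0.0456. With a 95% interval the printed rule then passes 0.03-0.06% (quantity) and 0.8-0.9% (consequences) of the time. The corrected rule rises to 25-31% and 6-7%. A valid non-inferiority test gains power with size; the printed one loses it.

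**6. Observed difference needed under the printed rule: M2 + z × SE.**

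- 95% interval, quantity: 0.247 to 0.275, which is 86-95% of 0.289.
- 95% interval, consequences: 0.207 to 0.235, which is 132-150% of 0.157.
- 90% interval: 0.22 to 0.24 (75-83%) and 0.18 to 0.20 (113-128%).

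**7. Size needed after correction.** With SD = 1, CAA = PNF, 80% power and one-sided 0.025: n per arm = 2(1.960 + 0.842)²/M2², about 4,587 for quantity and 45,867 for consequences. If repeated measures halved the SE (an assumption), about 1,147 and 11,467 would still be needed.

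**8. Units, as an illustration only.** Read as a log rate per week over 26 weeks (assumed for 6 months), the margins would be exp(0.0585 × 26) = 4.6 and exp(0.0185 × 26) = 1.6 as rate ratios. A d margin cannot be set directly against a coefficient of the written model.

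**The case against.** The strongest reply is that the intent is plain. The same paragraph speaks of a non-inferiority design, an acceptable loss and retention of half the effect, so this is a drafting slip in one sentence about a secondary aim. It also errs on the strict side and cannot produce a false claim of non-inferiority. All of that is true. It makes the repair easy, but the operative sentence still gives the wrong answer when followed.

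A second reply is that the sign changes little in practice. With a 95% interval and CAA = PNF, correction raises the pass probability by only about 7-8 percentage points for quantity and 2 for consequences; the larger obstacle is sample size against very small margins. This stands, and is why the power statement needs attention as well. The gain would be larger if CAA were truly better than PNF.

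A third reply concerns the SE. Section 10.2 plans a multiplicity correction over eight outcomes. If the stated power already used alpha = 0.05/8 (z = 2.734), the implied SE is 0.0736 to 0.0797. The printed rule then passes an equal CAA 0.3-0.4% and 1.4% of the time (95% interval), or 0.7-0.9% and 2.9-3.0% (90%). With a 95% interval the observed differences needed fall to 70-74% and 104-111% of the cited effects; with a 90% interval the consequences figure falls to 89-95%. So the comparison with the cited PNF effects depends on these choices. The finding that an equal CAA almost always fails does not.

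Finally, the log-link model and the statement "Time X CAA outcomes will provide direct tests of differences in change between CAA and control groups" belong to the Aim 1 text, and no Aim 2 model is written. The scale point is therefore a gap in specification. Nobody is likely to read d as a weekly slope, and the rate ratios above show only that a conversion is needed.

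**Conclusion.** The concern holds. The Aim 2 decision rule tests superiority by a margin and contradicts the plan's own definition of M2. Under every SE and interval level tried, it would declare a CAA equal to PNF non-inferior at most 3.5% of the time. With the sign corrected, power under equality is about 8-9% (quantity) and 4% (consequences) at one-sided 0.025, or 13-15% and 7% at one-sided 0.05, using the SE range of 0.096 to 0.111.

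The contradiction rests on the text alone. The probabilities rest on a normal approximation in d units and on applying the SE implied by section 10.1 to CAA versus PNF. The missing conversion to the d scale and the missing power for this contrast are secondary but belong to the same repair. This must be fixed before Aim 2 is analysed.

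**What to change.** In section 10.2, replace the decision sentence with: *Coded so that positive values favour CAA, CAA is declared non-inferior to PNF if the lower limit of the confidence interval for CAA minus PNF is greater than -0.0585 for drinking quantity and greater than -0.0185 for consequences.* The sponsor should confirm that CAA versus PNF is the intended contrast, as the text says.

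Also in section 10.2, name the confidence level and the time point, and state how the model contrast is put on the d scale, or how the margin is converted to a rate ratio, before the comparison.

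In section 10.1 and DSMP item 13, state that the given power does not apply to the Aim 2 contrast, and add the sponsor's own calculation for it. Report a missed margin as non-inferiority not shown, with the estimate and interval.

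The cost is a few sentences and one power calculation. No participants are added and the Aim 1 tests do not change. The drawback is that the plan would openly show low power for Aim 2. Timing matters: sections 7.5.1 and 7.5.2 show sessions running by March 2020, so the correction relaxes a success criterion after enrolment began. It should be a dated amendment with reasons, made before outcomes are compared by arm; if they have already been compared, the report should say so.

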2. PROJECT SUMMARY

We propose to evaluate the efficacy of a CAA-based intervention to change alcohol-related attitudes in support of moderate drinking. Specifically, heavy-drinking college students will be prompted to advocate for a counter-attitudinal topic (i.e., benefits of avoiding problems) by responding to a prompt asking them to detail how to avoid negative consequences by using self-generated protective behavioral strategies (PBS) and why this is a beneficial approach to drinking. With the understanding that their responses will inform future prevention programs, participants will then review their statements publicly with a research assistant. The new CAA intervention will be compared to (a) an assessment only (AO) control to determine absolute efficacy, and to (b) an empirically-supported personalized normative feedback (PNF)

intervention to determine relative efficacy, using a non-inferiority design. This study evaluates a novel intervention protocol linked to a clearly defined mechanism of behavior change and grounded in basic psychological research. If found to be efficacious, or at least non-inferior to the established PNF, the CAA approach will advance prevention science by targeting a separate and unique mechanism of change, and it will add to the toolbox of strategies available to colleges and universities to prevent harms related to drinking.

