8.2. Personalized Normative Feedback (PNF) Condition. Participants in the PNF condition will receive gender-identity specific personalized feedback regarding their alcohol use, consistent with previous NIAAA-funded trials using trained facilitator-delivered PNF as a brief intervention conducted by this team (e.g., R01AA014576). The PNF intervention contains both text and graphic information regarding 1) the student's own drinking quantity and frequency of drinking, 2) perceptions of typical drinking by same-sex students on campus (i.e., perceived descriptive norms), and 3) actual drinking rates by same-sex students' on campus (i.e., actual descriptive norms). Normative feedback for male or female identifying students will use data from same-sex students on campus, whereas normative feedback for non-binary or genderqueer students will use data averaged across all students on campus. The actual norms will be referenced to the survey from which norms were generated (date, N, and campus), which took place on both campuses in March 2019.

The RA will present the PNF sheets, populated by the participant's baseline data and will explain their format, where the normative data came from, and engage the participant in interpreting the graphic feedback. The RA will ask if the student has any questions about the information before concluding the session. This brief discussion is designed to be educational and clarifying, and to roughly equate the amount of interpersonal interaction to that in the CAA condition.

8.3. Assessment Only Control Condition. Participants in the assessment only control condition will receive no intervention. The only contact will consist of completing the baseline assessment in lab as well as email and telephone reminders to complete the 1-, 3-, and 6-month follow-up assessments.

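### The Aim 2 rule can declare CAA non-inferior to PNF, and count this in CAA's favour, without using the assessment-only arm to check that either intervention worked

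*Combined protocol and SAP*

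**What the plan says.** Section 10.2 takes the PNF effect from a published meta-analysis: "on drinking quantity ($d = .289$, 95% CI [0.117, 0.451"] for quantity and "consequences ($d = .157$, 95% CI[0.037, 0.278"] for consequences. The lower limits become M1, half of each becomes M2, and the aim is put as "we establish non-inferiority if we retain at least half of the effect of PNF". The decision is then: "if the lower bound confidence interval for the effect of CAA vs PNF is larger than half the lower bound estimate of the effects", with thresholds given as "drinking quantity (.117/2 = .0585) and consequences (.037/2 = .0185"), and in that event "we will be able to declare CAA is non-inferior to PNF".

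The trial also randomises 200 students to AO (section 6.1), and the section 10.2 model carries terms for PNF against control. The only comparison with AO that section 10.2 singles out as a direct test is CAA vs AO, under Aim 1. Aim 2 is not made conditional on Aim 1, or on PNF vs AO.

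The Project Summary (section 2) describes what follows from success: "If found to be efficacious, or at least non-inferior to the established PNF", CAA is to be added to the strategies available to colleges.

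**The concern.** A non-inferiority result supports a new intervention only if the comparator had an effect in the same trial. If PNF did nothing here, there is no effect to retain half of, and a result close to PNF is also close to no intervention. Two-arm trials must take the comparator's effect on trust. This trial need not, because it has a concurrent AO arm, but the rule does not use it.

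The documents give reasons to check the effect:

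- Aim 4b itself predicts that the response to PNF differs by site.
- The normative data come from a survey "which took place on both campuses in March 2019" (section 8.2), while sessions from March and April 2020 onward were remote, during and after campus closures (sections 7.5.1 and 7.5.2).
- The meta-analysis in the reference list concerns stand-alone PNF, whereas a research assistant presents and discusses PNF here (section 8.2).

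At stake is a favourable statement about CAA on an endpoint where nothing in the trial shows that either intervention beat assessment alone.

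**Working it through.** **Plan's own figures.** M2 = .117/2 = .0585 and .037/2 = .0185. Both reproduce.

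**Standard error of a two-arm contrast (assumed range, d units).** Section 10.1 allows 15% attrition (N = 510, so 170 per arm) and gives power .70, .80 and .90 at δ = .24, .27 and .32, without stating sidedness or within-person correlation.

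- Two-sided 5%: SE = δ/(1.96 + z_power). This gives .24/(1.96 + .5244) = .0966, .27/(1.96 + .8416) = .0964 and .32/(1.96 + 1.2816) = .0987. I use .0966.
- One measure, SD 1, 170 per arm: SE = √(2/170) = .1085. With a one-sided 5% test, power is .715, .801 and .904, which also matches the plan. With a two-sided test it is .600, .702 and .839, which does not.

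The range is therefore .0966 to .1085.

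**Decision rule.** I assume the lower limit of a two-sided 95% interval. The conventional rule requires that limit to exceed −M2. As written, it must exceed +M2. For a true CAA − PNF difference Δ:

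- sign corrected: P = Φ((Δ + M2)/SE − 1.96)
- literal: P = Φ((Δ − M2)/SE − 1.96)

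**Neither intervention works (Δ = 0).**

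| Endpoint | SE | Sign corrected | Literal |
|---|---|---|---|
| Quantity | .0966 | Φ(.606 − 1.96) = 8.8% | Φ(−.606 − 1.96) = 0.5% |
| Quantity | .1085 | Φ(.539 − 1.96) = 7.8% | Φ(−.539 − 1.96) = 0.6% |
| Consequences | .0966 | Φ(.192 − 1.96) = 3.9% | Φ(−.192 − 1.96) = 1.6% |
| Consequences | .1085 | Φ(.171 − 1.96) = 3.7% | Φ(−.171 − 1.96) = 1.7% |

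**PNF inert, CAA at d = .289, quantity.** Sign corrected: Φ(.3475/.0966 − 1.96) = 95% and Φ(.3475/.1085 − 1.96) = 89%. Literal: Φ(.2305/.0966 − 1.96) = 67% and Φ(.2305/.1085 − 1.96) = 57%.

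**Does Aim 1 catch the false cases?** I simulated 4 million three-arm trials with per-arm SE = contrast SE/√2 and the sign-corrected rule. When neither intervention works, CAA also fails to beat AO (unadjusted two-sided 5%) in about 88% of the quantity declarations and 84% of the consequences declarations.

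**Power of PNF vs AO, Φ(d/SE − 1.96).** At d = .289: 85% to 76%. At d = .157: 37% to 30%.

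**Effect of two possible conditions (same simulations, sign corrected; SE .0966, then .1085).**

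| Truth | Endpoint | Rule alone | PNF must beat AO | PNF or CAA must beat AO |
|---|---|---|---|---|
| Neither works | Quantity | 8.8%, 7.8% | under 0.01% | 1.0%, 1.0% |
| Neither works | Consequences | 3.9%, 3.7% | under 0.01% | 0.6%, 0.6% |
| PNF inert, CAA .289 | Quantity | 95%, 89% | 1.7%, 1.3% | 82%, 71% |
| Both .289 | Quantity | 8.8%, 7.8% | 4.9%, 3.1% | 8.7%, 7.5% |
| Both .157 | Consequences | 3.9%, 3.7% | 0.2%, 0.1% | 3.1%, 2.7% |

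**The case against.** The best reply is that Aim 1 already answers whether CAA works. CAA vs AO is the primary hypothesis, has multiplicity control, and covers consumption and consequences. Section 2 separates absolute efficacy (vs AO) from relative efficacy (vs PNF), and its sentence about being at least non-inferior is summary wording, not a decision rule. The margin is also already cautious: half of a lower 95% limit.

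Part of this stands. A careful reader would look at Aim 1. But nothing ties the two aims together, the summary offers non-inferiority as an alternative to efficacy, and in most of the false declarations CAA fails against AO too. A cautious margin discounts the historical effect; it does not verify it in this trial.

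Three stronger readings are tempting, and the documents do not support them.

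- *PNF did not work here.* The age of the norms and the move to remote sessions are reasons to check. No section shows a weakened effect.
- *A declaration without a significant PNF vs AO result means a failed comparator.* At d = .157 that test has 30% to 37% power. With so small a margin, CAA must also be observed about .17 to .19 better than PNF on consequences (1.96 × SE − .0185), which favours trials where PNF happened to do poorly. Such declarations would be common even if both interventions worked.
- *PNF must therefore beat AO before any claim.* That strict condition would all but remove a consequences claim when both work (3.9% to 0.2% at SE .0966), and would discard quantity results where CAA clearly beats AO.

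**Conclusion.** The concern holds as a gap in how a non-inferiority result is tied to the AO arm. The omission is in the text and does not depend on the arithmetic; it is present whether the margin is read as −M2 or, literally, as +M2.

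Its size is moderate. When nothing works, the false route is infrequent: about 8% to 9% for quantity and 4% for consequences with the sign corrected, and below 2% as literally written. When PNF is inert and CAA works at d = .289, declarations on quantity are the rule (89% to 95%, sign corrected). CAA's benefit is then real, but the claim to match an effective PNF is empty.

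These figures assume a two-sided 95% interval, normal estimates in d units, equal arms, and a contrast SE of .0966 to .1085. The weak power of the non-inferiority test and the sign of the margin are separate matters.

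**What to change.** In section 10.2, under Aim 2:

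1. Beside every non-inferiority result, report the PNF vs AO and CAA vs AO estimates with 95% confidence intervals, for the same endpoint and time point.
2. State that non-inferiority counts as support for CAA on an endpoint only if the AO arm shows an effect there: PNF better than AO, or CAA better than AO. Otherwise report the CAA vs PNF estimate and interval as not interpretable as evidence of efficacy.
3. State that PNF vs AO has about 76% to 85% power at d = .289 but only about 30% to 37% at d = .157, so a non-significant result does not show that PNF failed.
4. State the confidence level used for the non-inferiority bound.

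The Project Summary sentence should be brought into line with item 2.

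The cost is a few sentences. No new data, participants or model terms are needed, since the PNF and CAA contrasts with control are already fitted. The downside is fewer positive non-inferiority claims, mainly for consequences: with both interventions at d = .157, from 3.9% to 3.1% at SE .0966 and from 3.7% to 2.7% at SE .1085. In return, false support when neither works falls to about 1.0% (quantity) and 0.6% (consequences).

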6. STUDY POPULATION

6.1. Target Sample. The target sample for analyses is $N=600$ college student drinkers: 300 from Brown University, and 300 from the University of Houston. We will randomize 100 eligible students from each site to the CAA ($n=200$), PNF ($n=200$), and AO ($n=200$) conditions.

6.2. Inclusion Criteria. Inclusion criteria are:

(1) **Age 18-26.** The age range of 18-26 (a) coincides with the distinct developmental period of “emerging adulthood” (Arnett, 2005), (b) is characterized by a high prevalence of heavy episodic drinking (Johnson et al., 2012), and (c) is representative of college students, the majority of whom are 26 years of age or younger (Digest of Education Statistics: 2012).

(2) Male or female student at Brown University or University of Houston. The present study represents a first step in using counter-attitudinal advocacy activities in an attempt to reduce risky drinking behavior. As such, we focus on college students because they exhibit high rates of heavy episodic drinking (Johnson et al., 2012), and their identification with other college peers facilitates the testing of the enhanced manipulation. We recruit at 2 sites that differ in drinking patterns and demographics and geographic location to evaluate the generalizability of the study findings. The findings could have implications for alcohol abuse prevention both with college students and young adults more broadly.

(3) Past month heavy episodic drinking (for men, ≥ 5 drinks in one day, for women ≥ 4 drinks in one day). The 4/5 drink cutoff has been widely used as an indicator of risk ([name], Larimer, & Lewis, 2004; Wechsler & Nelson, 2001) and as a screening criterion in intervention studies targeting heavy drinking students. Our preliminary studies show that heavy drinking frequency is significantly correlated with attitudes towards moderate ($r = -.42$) and heavy ($r = .45$) drinking. By including only drinkers who have reported heavy episodic drinking we optimize the likelihood that developing arguments in favor of moderate drinking ($<4/5$ drinks/occasion) will constitute counter-attitudinal advocacy, and create dissonance between the espoused attitude in favor of moderation and recent behavior.

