Hypotheses associated with Aim 3 will evaluate mediators of intervention effects. We will follow procedures described by MacKinnon and colleagues (e.g., MacKinnon, Fairchild, & Fritz, 2007) to assess mediation. Mediation will test indirect effects using the AB products method with bootstrapped standard errors where A will represent effects of intervention contrasts by time interactions on mediators. B will represent the associations of mediators on subsequent drinking outcomes. Both A and B paths will control for baseline outcomes. Hypotheses associated with Aim 4 will follow a similar approach but will add prospective moderators and products of prospective moderators and contrasts

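### Aim 3 names only bootstrapped standard errors for the indirect effect; read literally, the test is conservative and can lose power that a percentile bootstrap interval would keep

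*Combined protocol and SAP*

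**What the plan says.** Section 10.2 (Analysis Plan) gives the Aim 3 method in a few lines. It defers to procedures in a cited mediation review and then states: "Mediation will test indirect effects using the AB products method with bootstrapped standard errors". The paths are defined as follows: "where A will represent effects of intervention contrasts by time interactions on mediators", and "B will represent the associations of mediators on subsequent drinking outcomes". Both paths adjust for baseline outcomes.

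The available text does not give a type of bootstrap interval, a reference distribution for AB over its standard error, a number of resamples, a resampling unit, or an alpha level for mediation. Bootstrapping is mentioned nowhere else. The analysis item of the Data and Safety Monitoring Plan (Appendix E, item 13) does not cover mediation, and no power is stated for Aim 3.

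**The concern.** A bootstrap standard error makes no normality assumption. A test that divides the estimate by that standard error and compares it with 1.96 does make one. The sampling distribution of a product of two estimates is skewed unless at least one path lies many standard errors from zero. With modest paths, the symmetric test therefore rejects too rarely. The same bootstrap draws give a percentile interval that follows the skew.

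The stake is the mechanism aim. A conservative test makes the predicted pathways harder to show. Aim 3 (Section 4) also predicts the absence of some pathways: norms for CAA, attitude change for PNF. The plan gives no separate criterion for those predictions. If a non-significant indirect effect is taken as support, a low-powered test makes them look confirmed too easily.

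**Working it through.** **Inputs from the plan**
- Allocation (Section 6.1): "We will randomize 100 eligible students from each site to the CAA ($n=200$), PNF ($n=200$), and AO ($n=200$) conditions".
- Attrition (Section 10.1): 15%, N = 510. So 510/3 = 170 per arm and 2 × 170 = 340 per pairwise contrast.
- Anticipated effect on outcomes relative to control (Section 10.1): "which are typically in the .28 range".
- Attitude–drinking association (Section 6.2): "heavy drinking frequency is significantly correlated with attitudes towards moderate ($r = -.42$) and heavy ($r = .45$) drinking".

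**Assumptions, because the plan is silent**
- A (standardised mean difference on the mediator): .28 as a proxy, with .40 and .50 as larger values.
- B (standardised): .14 to .42, the top being the cross-sectional correlation.
- Two-sided alpha of .05.

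**The plan's own power figure.** It concerns intervention contrasts, not mediation: .70, .80 and .90 at δ = .24, .27 and .32.
- 170 per arm, one measure, two-sided .05: .600, .702, .839. Not reproduced.
- One-sided .05: .715, .801, .904. Reproduced within 2 points.
- Two-sided .05 on the mean of three measures, assumed intraclass correlation .7: .696, .795, .910. Also reproduced.

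The plan does not say which route was used. The 170 per arm is consistent with its figures.

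**Why the SE-based test falls short.** Large-sample formulas with n = 340:
- s_A = 2/√340 = .1085
- s_B = √(1 − B²)/√340
- SE(AB) = √(A²s_B² + B²s_A² + s_A²s_B²)

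At A = .28, B = .15:
- s_B = .0536, so A/s_A = 2.58 and B/s_B = 2.80. Each path alone clears 1.96.
- AB = .042 and SE(AB) = √(.000225 + .000265 + .000034) = .0229.
- AB/SE = 1.83, below 1.96.

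At A = .28, B = .42:
- s_B = .0492 and B/s_B = 8.53.
- AB = .1176 and SE(AB) = .0479.
- AB/SE = 2.46, close to the 2.58 for A alone. The penalty has almost gone.

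**Power at n = 340.** The model was a continuous mediator and outcome, two arms, one mediator. The main simulation used 1,500 datasets with 800 participant resamples each. Ranges span it and separate simulation or large-sample checks.

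| A | B | AB/SE against 1.96 | 95% percentile interval | Gain (points) |
|---|---|---|---|---|
| .28 | .14 | .27–.28 | .51–.52 | 23–26 |
| .28 | .15 | .31 | .53–.57 | 22–26 |
| .28 | .20 | .51 | .69–.70 | 18–19 |
| .28 | .30 | .66–.68 | .72–.74 | 5–7 |
| .28 | .42 | .71–.73 | .74–.75 | 2–3 |
| .40 | .20 | .79–.82 | .90–.92 | 9–11 |
| .50 | .30 | .993 | .997 | <1 |

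Without attrition (400 per contrast, A = .28), the large-sample check gives .37 vs .61, .64 vs .79, .76 vs .80 and .79 vs .81 at B = .14, .20, .30 and .42.

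**False positives** (SE-based / percentile / bias-corrected, main simulation)
- Both paths zero: .000 / .000 / .003
- A = .28, B = 0: .013 / .041 / .073
- A = 0, B = .42: .036 / .047 / .055

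A separate simulation gave percentile rates of .036 to .064, near 5% within simulation error.

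**If the planned model adds precision.** Suppose a baseline correlation of .6, so that s_A is multiplied by √(1 − .6²) = .8, and B is estimated on all 510. With A = .28, power is .65 vs .82 at B = .15, .81 vs .89 at .20, .88 vs .90 at .30 and .88 vs .89 at .42. With A = .40 and B = .20 it is .98 vs .99.

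**The case against.** The strongest reply is that the defect is inferred. Section 10.2 never says that AB will be divided by its standard error and compared with a normal quantile. It defers to a cited mediation review that cannot be consulted here, and the wording may be shorthand for bootstrap intervals. In that case there is no power loss. This stands: a reader might infer that the plan has committed itself to a normal reference for the product, but the text does not establish it. What remains is that the literal wording permits the weaker test, and two analysts could reach different conclusions from the same draws.

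The second reply is that a large loss depends on weak assumed paths. This also stands. The only B anchor in the documents is a correlation of about .42 to .45, where the two methods differ by 3 points or less. The .28 is an effect on outcomes. Mediators are measured immediately after the session (Section 5), so A could be larger. In the other direction, a prospective B adjusted for baseline could fall well below a cross-sectional correlation.

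The third is that the simulation is not the planned analysis. It leaves out the repeated measures, the baseline adjustment and the negative binomial mixed model. The precision check above shows that the gap mostly closes, though 17 points remain at A = .28, B = .15.

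Finally, the percentile interval does not rescue a weakly powered pathway: at A = .28, B = .15 it reaches only .53 to .57.

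**Conclusion.** The concern holds in limited form. The plan should name its decision rule for AB, and the percentile interval is the better rule at almost no cost. Read literally, the stated method loses about 18 to 26 points of power at A = .28 with B of .14 to .20, 5 to 7 points at B = .30, and 3 points or less at B = .42 or at A = .50 with B = .30. These figures rest on assumed path sizes, a two-sided 5% level, 340 per contrast and a simplified continuous model. They would probably be smaller under the full model.

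Two stronger readings are not supported. One is that the plan certainly gives up a large share of its mediation power: that is true only for weak paths, whose sizes the documents do not give. The other is that mediation findings would be unsafe: the SE-based test is conservative, so a significant indirect effect is not made less trustworthy by this choice. Aims 1 and 2 are unaffected.

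**What to change.** In the Aim 3 paragraph of Section 10.2, replace the reference to bootstrapped standard errors with a decision rule. Each indirect effect is judged by whether its 95% percentile bootstrap confidence interval excludes zero. Participants are resampled with all their repeated measures together, and the number of draws (for example 5,000) and the seed are stated.

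The percentile form is preferable to the bias-corrected form, which gained more power but reached .073 false positives with B = 0.

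The cost is one sentence, with no new data and no larger sample; more draws cost only computing time. The trade-off is that false-positive rates move closer to 5% than under the SE-based test.
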